Treatment comparisons will also be made separately for each time point and dose using logistic regression model including fixed effects of baseline BDCVA at 40 cm as a covariate and treatment, Pearson's chi-squared test or Fisher's exact test if any of the cell counts are less than five as a sensitivity analysis to the primary model above.

Secondary Efficacy Analysis

For the secondary efficacy endpoints of BDCVA at 40 cm, the percentage of subjects who achieve a ≥ 3 -line (15-letters) improvement from baseline without a loss of ≥ 5 letters in best distance corrected VA at 4m for each Visit, time point and daily dose (Dose 1 and Dose 2) will be summarized and analyzed using the same imputation as the primary efficacy endpoint. The same modeling strategy will be used as detailed in the primary efficacy analysis for any time point that is measured after both doses within the visit [e.g.: 2 hours at Visit 3 (Day 8); 30 minutes, 1 and 2 hours at Visit 2 (Day 1); and 20 minutes, 1, 2, and 3 hours at Visit 4 (Day 15)]. For those time points that are measured only after the second dose within the visit [REDACTED]

[REDACTED]

[REDACTED]

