3.1 Overall Study Design

This is a four-visit multi-center, randomized, double-masked, parallel-group study evaluating the safety and efficacy of CSF-1 compared with Vehicle in approximately 300 subjects with presbyopia. The study design is summarized in [Figure 1](#).

Visit 1 (Screening, Day -14 to -1): Qualified subjects will receive 1 drop of Vehicle instilled in each eye, followed by preliminary efficacy assessments to identify Vehicle responders at 15 minutes post-vehicle instillation.

Vehicle responder is defined as a subject who had a > 0.14 LogMAR (i.e., 7 letters) improvement in post-Vehicle treatment (at 15 minutes post-Vehicle treatment) monocular BDCVA in either eye at 40 cm compared to Visit 1 pre-treatment, or a > 0.14 LogMAR (i.e., 7 letters) improvement in monocular BDCVA in either eye at 40 cm between Visit 1 (pre-treatment) and Visit 2 (pre-treatment baseline).

Visit 2 (Day 1): Baseline assessments. Subjects who meet all inclusion and none of the exclusion criteria and qualify as Vehicle non-responders, will be randomized 1:1 to one of the following treatment arms:

- CSF-1 (0.4% pilocarpine hydrochloride ophthalmic solution)
- Vehicle

Pre-treatment measurements taken at this visit are considered as baseline.

[figure not shown]
At the Visit 2 (Day 1) clinic visit, study personnel will instill Dose 1 of study drug at 8:30 AM \pm 30 minutes in each eye. Efficacy and safety assessments will be conducted for 2 hours following Dose 1. Dose 2 will be instilled by study personnel at 10:30 AM \pm 30 minutes in each eye. Efficacy and safety assessments will be conducted for 4 hours following Dose 2.

All subjects will be instructed to dose twice daily (BID) with a single drop in each eye for approximately 1 week. The first daily dose should occur in the morning, with the second dose following 2 hours later (± 1 hour). Subjects will be instructed not to dose at home on clinic visit days.

Visit 3 (Day 8): Study personnel will instill Dose 1 of study drug at 8:30 AM \pm 30 minutes in each eye. Efficacy and safety assessments will be conducted for 2 hours following Dose 1. Dose 2 will be instilled by study personnel at 10:30 AM \pm 30 minutes in each eye. Efficacy and safety assessments will be conducted for 2 hours following Dose 2.

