4.2 Masking and Unmasking

An independent, unmasked biostatistician who is not otherwise involved in the trial will generate the complete randomized study drug kit list. The subject, study sponsor, medical investigators, and study staff will be masked during the entire randomization process and throughout the course of the study. When medically necessary, the investigator may need to determine what treatment has been assigned to a particular subject. When possible (i.e., in non-emergent situations), [REDACTED] and/or the study sponsor should be notified before unmasking the IP. In emergency situations, the investigator must notify the sponsor within 24 hours after determining that it is necessary to unmask the treatment assignment. The investigator must also indicate in source documents and in the electronic case report form (eCRF) that the mask was broken and provide the date, time, and reason for breaking the mask.

5. Sample Size and Power Considerations

A total sample size of 280 subjects (140 subjects per arm) yields > 97.5% power to establish superiority of CSF-1 to Vehicle in the percentage of study eyes demonstrating a \geq 3-line (15-letter) gain from baseline in BDCVA at 40 cm (Precision Vision chart) and no loss of BDCVA \geq 5 letters (ETDRS at 4 m), 1-hour post

each dose on Visit 3 (Day 8) assuming a response rate of 42.5% in CSF-1 and 17.5% in Vehicle using a Pearson chi-squared test with a 2-sided significance level of 0.05.

A series of horizontal black bars of varying lengths, likely representing redacted text or data. The bars are arranged vertically and span the width of the page. Some bars are longer, while others are shorter, indicating different lengths of redacted content.

Accounting for approximately a 5% discontinuation rate, approximately 150 subjects per arm (approximately 300 total) will be randomized.

6. Data Preparation

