7.1 Full Analysis Set

The full analysis set (FAS) will include all randomized subjects who have received at least one dose of the study drug. Subjects in the FAS will be analyzed as randomized. The FAS analysis set will be the primary analysis set for the determination of efficacy.

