8.5 Adjustment for Multiplicity

If the primary null hypothesis, H_{01} , is rejected at a 2-sided alpha = 0.05 in favor of CSF-1 in the alternative hypothesis, H_{11} , tested as delineated in the primary efficacy analysis section ([Section 12.1](#)), then the study will be considered a success and the following key secondary hypotheses will be tested in hierarchical order, each at a 2-sided alpha = 0.05, where inference will be made on each null hypothesis only if the prior null hypotheses are rejected in favor of CSF-1.

1. Visit 3 (Day 8), 2 hours following Dose 1 (H_{02})
2. Visit 3 (Day 8), 1 hour following Dose 2 (H_{03})
3. Visit 3 (Day 8), 2 hours following Dose 2 (H_{04})

9. Disposition of Subjects

Subject disposition will be presented in terms of the numbers and percentages of subjects who were randomized, completed the study, and discontinued from the study. A discontinued subject is someone who does not complete the 4 protocol-defined study visits. Subjects who are not discontinued from the study will be considered study completers. Disposition will be summarized by treatment arm for all randomized subjects. The reasons for study discontinuation will also be summarized and include: AE, lost to follow-up, physician decision, protocol violation, study terminated by sponsor, withdrawal by subject, death, and other. A subject listing will be provided which includes the date and reason for study discontinuation.

The number of subjects in each of the analysis sets (FAS, PPS, and SAF) will be displayed by treatment arm, with the number of subjects and percentages calculated using randomized subjects as the denominator. The number and percentage of subjects with any (major, or minor) protocol deviations will be summarized by treatment arm and overall for all randomized subjects. Protocol deviations will be classified as major or minor prior to the closure of the database during a masked review of each protocol deviation. Major deviations will be defined as those deviations that potentially affect the analysis of the primary study endpoint.

A subject listing will be provided which includes the date of the deviation, the deviation code and description, and the classification of whether the deviation was deemed major or minor. In addition, subject listings will include treatment arm and ICF signature date, and exclusions from the PPS. There will also be a listing of screen failures.

10. Demographic and Baseline Characteristics

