12.1 Primary and Key Secondary Efficacy Analysis

The primary efficacy endpoint in this study is the percentage of subjects with a ≥ 3 -line (15-letter) gain, from baseline, in best distance-corrected visual acuity (BDCVA) at 40 cm (Precision Vision chart) and no loss in BDCVA ≥ 5 letters (ETDRS chart) at Visit 3, 1 hour following Dose 1 in the study eye. The key secondary efficacy endpoints are defined the same as the primary efficacy endpoint, except for being measured at 2 hours following Dose 1, 1 hour following Dose 2, and 2 hours following Dose 2, all at Visit 3.

The primary and key secondary efficacy analysis will be conducted in the FAS with missing data handled in the following manners:

1. Discontinuation of study drug and non-optimal compliance will be ignored [treatment policy strategy].
2. Withdrawal due to lack of efficacy or AEs: missing data will be singly imputed as failure [hypothetical strategy].
3. Missing data without withdrawal or withdrawal due to reasons other than lack of efficacy or AEs: missing data will be imputed employing Multiple Imputation (MI) using randomized treatment-based Markov Chain Monte Carlo (MCMC) methods.

No subject data will be excluded from the FAS due to protocol violations/deviations. The multiple imputation of missing values will be completed for the continuous measures (BDCVA at 40 cm and BDCVA at 4 m), then the response variable will be determined therefrom. Imputation of failure due to lack of efficacy or AE will be assigned after multiple imputation is performed.

Variables for treatment group, baseline for BDCVA at 40 cm and baseline for BDCVA at 4 m will also be included in the multiple imputation model. 25 complete imputed datasets will be created.

Example SAS® code for the multiple imputation:

```
PROC MI DATA=DATAIN OUT=MI NIMPUTE=25 SEED=118787 minimum=-0.3 maximum=1;
  MCMC INITIAL=EM;
  VAR TRTPN VA40 VA40BL VA4 VA4BL;
RUN;
```

Where TRTPN = treatment group, coded 1 for CSF-1, else 0

VA40 = value of BDCVA at 40 cm for Visit 3, 1 hour after Dose 1

VA40BL = baseline value of BDCVA at 40 cm

VA4 = value of BDCVA at 4 m for Visit 3, 1 hour after Dose 1

VA4BL = baseline value of BDCVA at 4 m

For each imputed dataset, a logistic regression model with baseline BDCVA at 40 cm as a covariate and treatment as a main effect will be used to obtain the treatment effect estimate, odds ratio, and 95% confidence interval (CI) for odds ratio.

Example SAS® code for the logistic model is shown here:

```

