14.2 Best Distance-Corrected Visual Acuity

Safety variables include BDCVA at 4 m under normal and low-luminance testing conditions.

Monocular BDCVA summaries will specify study eye and fellow eye. Monocular BDCVA and Low-Luminance BDCVA (LL-BDCVA) at 4 m will be measured at pre-treatment, post-Dose 1 and post-Dose 2 as mentioned in the schedule of assessments ([Section 3.2](#)). The observed BDCVA as well as the change from baseline in BDCVA and LL-BDCVA will be summarized by treatment group using continuous descriptive summary statistics, and subject-specific BDCVA and LL-BDCVA data will also be presented in a listing for each visual range, separately. Tables will also provide the number and percentage of eyes that lose 10 or more letters BCDVA at 4 m.

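### The imputation model in SAP 12.1 leaves out Day 1 on-drug acuity; adding it as auxiliary data is a minor, cheap improvement, not the correction of an error.

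*SAP*

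**What the plan says.** SAP 12.1 states the imputation model in prose and in example code, and the two agree. The prose says that the continuous acuities at 40 cm and 4 m are imputed, and adds: "Variables for treatment group, baseline for BDCVA at 40 cm and baseline for BDCVA at 4 m will also be included". The code line is "VAR TRTPN VA40 VA40BL VA4 VA4BL", with VA40 and VA4 defined as the Visit 3 values 1 hour after Dose 1. No reading from any other post-dose time point enters.

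Multiple imputation covers data missing without withdrawal, and withdrawals for reasons other than lack of efficacy or adverse events. Withdrawals for those two reasons are overwritten as failures after imputation.

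Day 1 on-drug readings should exist for almost everyone analysed:
- SAP 7.1 defines the full analysis set as "all randomized subjects who have received at least one dose of the study drug".
- SAP 3.1 has staff instil Dose 1 in clinic at Visit 2, after which "Efficacy and safety assessments will be conducted for 2 hours following Dose 1".
- Protocol 10.7 (Secondary Efficacy Analysis) applies the composite response, which needs both distances, at "30 minutes, 1 and 2 hours at Visit 2 (Day 1").
- SAP 14.2 adds for distance acuity: "Monocular BDCVA and Low-Luminance BDCVA (LL-BDCVA) at 4 m will be measured at pre-treatment, post-Dose 1 and post-Dose 2".

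**The concern.** An imputation is only as good as the missing-at-random assumption behind it. Here, missingness must be unrelated to the Visit 3 outcome given treatment and baseline alone. Missing at random given baseline and the response already seen on Day 1 is easier to defend, because Day 1 response on the same drop is likely to predict Day 8 response.

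There is a plausible route for selective missingness. The failure rule is meant to catch subjects who leave because the drops did not work, yet lack of efficacy is not among the discontinuation reasons in SAP 9 or the withdrawal reasons in protocol 5.3. Such a subject could be recorded as a withdrawal by subject or as other, and so reach the imputation step. The model would then give that subject about the arm's response rate and ignore the Day 1 non-response on file. At stake is a small shift in the reported treatment effect and slightly more imputation error than necessary.

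**Working it through.** **Plan's own figure.** Inputs from SAP 5 and protocol 10.5: 140 per arm, 42.5% v 17.5%, two-sided 0.05, Pearson chi-squared. With pooled rate 0.30, z = [0.25√140 − 1.96√(2×0.30×0.70)] / √(0.425×0.575 + 0.175×0.825) = (2.958 − 1.270)/0.6235 = 2.71. Power is 99.7%, consistent with the stated lower bound of 97.5%. For dropout, 140/0.95 = 147.4, so 148, in line with about 150.

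**Amount missing.** SAP 5 says: "Accounting for approximately a 5% discontinuation rate". SAP 9 says: "A discontinued subject is someone who does not complete the 4 protocol-defined study visits". The 5% therefore runs to Day 15 and is an upper case for Day 8. 5% of 150 is 7.5, taken as 8 per arm.

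**Bias formula.** Let m be the share missing and imputed, p the arm rate, and q the true Day 8 response rate of those missing. The model imputes at about p, so the arm's rate is overstated by m(p − q). *Assumptions, not in the documents:* all missing subjects reach imputation; all were Day 1 non-responders; Day 1 and Day 8 are bivariate normal with correlation 0.4, 0.6 or 0.8.

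| Correlation | q, CSF-1 | q, Vehicle | CSF-1 only: 0.05×(42.5−q) | Vehicle only: −0.05×(17.5−q) | Both arms |
|---|---|---|---|---|---|
| 0.4 | 31.4% | 13.7% | +0.55 | −0.19 | +0.36 |
| 0.6 | 25.2% | 11.2% | +0.87 | −0.32 | +0.55 |
| 0.8 | 17.5% | 7.9% | +1.25 | −0.48 | +0.77 |

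Allowing a 4 m loss rate of 0.4% to 5% lowers these by at most 0.04 points. At 2.5% missing each figure halves.

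**Scale.** The sampling SE of the difference is √(0.425×0.575/150 + 0.175×0.825/150) = 5.1 points. SAP 12.1 reports an odds ratio. For CSF-1-only selection, dividing by 0.425×0.575 = 0.244 gives 0.0055/0.244 = 0.02, 0.0085/0.244 = 0.035 and 0.0125/0.244 = 0.05 on the log odds ratio. Its SE is √(1/(150×0.244) + 1/(150×0.144)) = 0.27 (0.28 with imputation), so the shift is under 0.2 SE.

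**Simulation.** 150 per arm, 8 per arm missing both Visit 3 acuities, the SAP's bounds of −0.3 and 1, 15 imputations, 4,000 replicates. In the one-arm rows, the other arm is missing at random.

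| Selection on Day 1 response | SAP model bias at 0.4/0.6/0.8 (points) |
|---|---|
| Both arms, all non-responders | +0.37/+0.58/+0.85 |
| CSF-1 only | +0.59/+0.93/+1.31 |
| Vehicle only | −0.23/−0.37/−0.54 |
| Both arms, non-responders twice as likely to be missing | +0.09/+0.14/+0.23 |
| Completely random | −0.03/−0.02/−0.01 |

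With the two Day 1 variables added, bias was 0.04 points or less in absolute value in all 15 settings. A second simulation (25 imputations; correlations 0.3, 0.6 and 0.8) showed how it arises. Missing CSF-1 Day 1 non-responders were imputed as responders 40% to 41% of the time under the SAP model. With the Day 1 variables they were imputed at 33%, 23% and 16%, against true rates of 35%, 24% and 17%.

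**Gain if missingness is completely random.** Error against complete data is 1.21 to 1.24 points (SAP model) v 0.92 to 1.18 (with Day 1). Combined with the sampling SE, total error falls by between 1 − √(5.1²+1.18²)/√(5.1²+1.21²) = 0.1% and 1 − √(5.1²+0.92²)/√(5.1²+1.24²) = 1.3%.

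**Planned worst case (SAP 12.2).** At the planned rates, 142 observed per arm give 60 and 25 responders. Setting 8 missing CSF-1 subjects to failure and 8 missing Vehicle subjects to success gives 60/150 v 33/150, p = 0.0008 (unadjusted chi-squared).

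**The case against.** The strongest reply is that nothing here is wrong. The model is prespecified, its prose and code agree, and it holds treatment, both baselines and both outcome components. Where only one of the two acuities is missing, it does use the other. That stands: this is a modelling choice that can be improved.

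The failure rule and the sensitivity analyses also remove much of the risk. This stands in part. Adverse-event withdrawals bypass imputation, but lack-of-efficacy withdrawals may not be recorded as such. The missing-as-failure, observed-data and tipping-point analyses show how robust the conclusion is, but none uses Day 1 data, so none corrects the primary estimate.

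The evidence has limits. The assessment schedules are not legible in the public documents, so Day 1 collection at 1 hour at both distances rests mainly on an illustrative list in protocol 10.7. The correlations and the missingness pattern are assumed.

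A reader might infer something stronger: that the omission biases the trial towards CSF-1, or by several points. The documents do not support this. Direction depends on which arm's non-responders are missing. The largest possible errors at 5% missing, 0.05×(42.5+82.5) = +6.25 and −0.05×(57.5+17.5) = −3.75 points, hold for any missingness mechanism. They do not come from this omission, and Day 1 data would not remove them. Larger figures also follow if CSF-1 non-responders and Vehicle responders go missing together, but nothing in the documents suggests that pattern.

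**Conclusion.** The point holds as a low-priority improvement. The omission creates bias only if missingness depends on Day 1 response, on which the documents are silent. If every missing subject were a Day 1 non-responder at 5% per arm, the bias in the difference would be about +0.35/+0.55/+0.75 points (both arms), +0.55/+0.85/+1.25 (CSF-1 only) or −0.2/−0.3/−0.5 (Vehicle only) at correlations 0.4/0.6/0.8. With milder selection (non-responders twice as likely to be missing) it is +0.1 to +0.25 points. If missingness is completely random, the only gain is 0.1% to 1.3% less total error. Against a planned 25-point difference, the success conclusion is very unlikely to change. The benefit is a more defensible missing-at-random assumption and a slightly better effect estimate.

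**What to change.** Before unmasking, add the study eye's Visit 2 BDCVA at 40 cm and at 4 m, 1 hour after Dose 1, to the imputation model as auxiliary variables, giving seven variables in all. Do this for the primary endpoint and for H02 to H04. Where only one Visit 3 time point is missing, also use the subject's other Visit 3 readings, which are the closest information available. Keep the overwrite to failure after imputation.

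No new data are needed. The cost is an amendment to a SAP already at version 2.0, two or more extra variables, and a check of MCMC convergence. In a trial run of the seven-variable model with 300 subjects and a non-monotone pattern, lag-1 autocorrelation was 0.04 or less, so convergence should not be a difficulty.

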10.7 Efficacy Analysis

Primary Efficacy Analyses

The primary efficacy endpoint in this study is the percentage of subjects with a ≥ 3 -line (15-letter) gain, from baseline, in best distance-corrected visual acuity (BDCVA) at 40 cm (Precision Vision chart) and no loss in best distance corrected visual acuity ≥ 5 letters (ETDRS chart) at Visit 3, 1 hour following Dose 1 in the study eye. The primary efficacy analysis will be conducted in the FAS with intercurrent events handled in the following manners:

- 1) Discontinuation of study drug and non-optimal compliance will be ignored [treatment policy strategy].
- 2) Withdrawal due to lack of efficacy or adverse events: missing data will be singly imputed as failure [hypothetical strategy].
- 3) Missing data without withdrawal or withdrawal due to reasons other than lack of efficacy or adverse events: missing data will be imputed employing Multiple Imputation (MI) using randomized treatment-based Markov Chain Monte Carlo (MCMC) methodology [hypothetical strategy].

No subject data will be excluded from the FAS due to protocol violations/deviations. The FAS will be used for the primary efficacy analyses. Note that multiple imputations of missing values will be completed for the continuous measures (BDCVA at 40 cm and best distance corrected VA at 4m), then the response variable will be determined therefrom.

[REDACTED]

Descriptive statistics will be presented by treatment group. Testing of the percentage of subjects with at least a 3-line (15-letter) improvement from baseline in BDCVA at 40 cm without a loss of ≥ 5 letters in best distance corrected VA at 4m will be completed separately for the 1 hour and 2 hour time points using a generalized linear mixed model with a binomial distribution including fixed effects of baseline BDCVA at 40 cm as a covariate, daily dose (Dose 1 and Dose 2), treatment, and the interaction of dose with treatment and random effect of subject to account for the correlation within a subject between daily doses. [REDACTED]

[REDACTED]

The adjusted odds ratios and marginal proportions and difference in proportions along with corresponding two-sided 95% Confidence Intervals (CIs) and p-values will be presented.

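### The imputation model gives both arms one residual spread and one baseline slope, so unequal spreads could shift imputed responder rates slightly in either direction; imputing within arm avoids this and settles what treatment-based means

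*SAP*

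**What the plan says.** For data missing without withdrawal, or after withdrawal for reasons other than lack of efficacy or adverse events, SAP 12.1 calls for "Multiple Imputation (MI) using randomized treatment-based Markov Chain Monte Carlo (MCMC) methods". Protocol 10.7 has almost the same phrase, "using randomized treatment-based Markov Chain Monte Carlo (MCMC) methodology". Neither defines it further.

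SAP 12.1 then says how treatment enters: "Variables for treatment group, baseline for BDCVA at 40 cm and baseline for BDCVA at 4 m will also be included in the multiple imputation". The example code is one call, "PROC MI DATA=DATAIN OUT=MI NIMPUTE=25 SEED=118787 minimum=-0.3 maximum=1", with the variable list "VAR TRTPN VA40 VA40BL VA4 VA4BL" and the coding note "Where TRTPN = treatment group, coded 1 for CSF-1, else 0". It has no BY statement and no treatment interaction.

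The imputed quantities are the continuous acuities at 40 cm and 4 m, and response is derived from them afterwards. SAP 8.4 sets the cut-offs: a change of -0.30 logMAR or lower at 40 cm, and no worsening of 0.10 logMAR or more at 4 m. For withdrawals due to lack of efficacy or adverse events, "Imputation of failure due to lack of efficacy or AE will be assigned after multiple imputation is performed". The same rules cover the primary endpoint and the three key secondary endpoints.

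**The concern.** In a multivariate-normal model, a 0/1 treatment variable moves only the mean of the other variables. Given treatment, both arms share one residual covariance matrix and one regression of post-dose acuity on baseline.

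For an analysis of mean acuity this would matter little. Here each imputed value is cut at a threshold, and the chance of passing the threshold depends on the spread around the mean. If the true spreads differ, the shared model makes the less variable arm too wide and the more variable arm too narrow. The imputed responder rates are then wrong even when data are missing at random and both arm means are right. The same model would feed the primary test of H01 and the tests of H02 to H04.

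There is also a question of wording. *Randomized treatment-based* can mean that treatment is a covariate, or that each arm is imputed separately. The two give different results when spreads differ, and the choice should not be left open in a confirmatory analysis.

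**Working it through.** **Inputs from the documents.** Response rates of 42.5% (CSF-1) and 17.5% (Vehicle), 140 per arm, Pearson chi-squared test at two-sided 0.05, about 5% discontinuation and about 150 randomized per arm (SAP 5); 1:1 allocation (SAP 4.1); the -0.30 and 0.10 logMAR cut-offs (SAP 8.4).

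**Assumed, because the documents do not give them.** Normally distributed changes; SD ratio r = SD(CSF-1) / SD(Vehicle) from 0.5 to 2; 5% or 10% of Visit 3 values imputed, equally in both arms.

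**The plan's own figure.** With mean rate 0.30:
- null SE = sqrt(2 × 0.30 × 0.70 / 140) = 0.05477
- alternative SE = sqrt((0.425 × 0.575 + 0.175 × 0.825) / 140) = 0.05270
- power = Φ((0.25 − 1.96 × 0.05477) / 0.05270) = Φ(2.71) = 99.66%

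This agrees with the stated figure of more than 97.5%. Allowing for dropout, 140 / 0.95 = 147.4, or 148, agrees with about 150.

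**Closed form, near-vision criterion only.** Set Vehicle SD to 1 and CSF-1 SD to r. Place each mean so that the true rates hold: Φ⁻¹(0.175) = −0.9346 and Φ⁻¹(0.425) = −0.1891. With equal arms the common SD is s = sqrt((1 + r²) / 2). The imputed rates are then

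- Vehicle: Φ(−0.9346 / s)
- CSF-1: Φ(−0.1891 × r / s)

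The shift in the full-sample difference is the missing fraction times (imputed difference − 25 points).

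For r = 2: s = 1.581; Vehicle Φ(−0.591) = 27.7%, CSF-1 Φ(−0.239) = 40.5%, difference 12.8; 0.05 × (12.8 − 25) = −0.61 point.

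For r = 0.5: s = 0.791; Vehicle Φ(−1.182) = 11.9%, CSF-1 Φ(−0.120) = 45.2%, difference 33.4 before rounding; 0.05 × (33.4 − 25) = +0.42 point.

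| r | Imputed Vehicle | Imputed CSF-1 | Shift, 5% missing | Shift, 10% missing |
|---|---|---|---|---|
| 0.50 | 11.9% | 45.2% | +0.42 | +0.84 |
| 0.67 | 13.6% | 44.1% | +0.27 | +0.55 |
| 0.80 | 15.1% | 43.4% | +0.16 | +0.33 |
| 1.00 | 17.5% | 42.5% | 0.00 | 0.00 |
| 1.25 | 20.4% | 41.7% | −0.19 | −0.37 |
| 1.50 | 23.2% | 41.2% | −0.35 | −0.70 |
| 2.00 | 27.7% | 40.5% | −0.61 | −1.22 |

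**Simulation.** 1,200 trials per scenario, 150 per arm, 5% missing completely at random, 10 imputations, Bayesian multivariate-normal draws within the −0.3 to 1 bounds, and both parts of the responder rule. Baseline means and SDs (0.5 and 0.1 near, −0.05 and 0.07 distance) and a distance residual SD of 0.05 were assumed. Shifts are in points, against the same trials with no data missing.

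| SD Vehicle / CSF-1 | Baseline slope of change, Vehicle / CSF-1 | Shared model | Within arm |
|---|---|---|---|
| 0.12 / 0.12 | 0 / 0 | −0.03 | −0.02 |
| 0.10 / 0.15 | 0 / 0 | −0.33 | 0.00 |
| 0.15 / 0.10 | 0 / 0 | +0.21 | −0.05 |
| 0.08 / 0.16 | 0 / 0 | −0.62 | −0.06 |
| 0.16 / 0.08 | 0 / 0 | +0.41 | +0.03 |
| 0.12 / 0.12 | 0 / −0.5 | −0.09 | −0.03 |
| 0.12 / 0.12 | −0.5 / 0 | +0.05 | +0.01 |
| 0.08 / 0.16 | 0 / −0.5 | −0.64 | −0.05 |

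The simulation agrees with the closed form. Unequal slopes with equal spreads move the difference by 0.1 point or less. Imputing within arm stays within 0.1 point of the full-data result throughout.

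**Consequence.** In the worst closed-form case (r = 2, 10% missing; rates 42.30% and 18.52%), chi-squared power at 150 per arm is still 99.5%. On the odds-ratio scale of the planned model, without baseline adjustment, the assumed rates give (0.425 / 0.575) / (0.175 / 0.825) = 3.48. With 5% missing, r = 2 gives (0.4240 / 0.5760) / (0.1801 / 0.8199) = 3.35, and r = 0.5 gives (0.4264 / 0.5736) / (0.1722 / 0.8278) = 3.57.

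**The case against.** The strongest reply is that this is a choice between two acceptable models and that it hardly matters. About 5% of 150 is 7.5 subjects per arm, and some of those will be scored as failures rather than imputed. SAP 12.2 also plans missing-as-failure, observed-data (FAS and PPS) and tipping-point analyses, none of which uses this imputation model. The tipping point starts from every missing CSF-1 record failing and every missing Vehicle record succeeding, which is far harsher than a shared variance. The code is labelled as an example.

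All of that stands as to size. It does not remove the point: SAP 8.2 makes those analyses supportive, so they show robustness without correcting the primary estimate. Calling the code an example does not help either, because the text beside it also describes treatment as a variable in the model and says nothing of separate models.

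A reader might infer two stronger things. The first is that the model overstates Vehicle responders and so works against CSF-1. That needs CSF-1 acuity to be the more variable. Uneven response to the drug would make this plausible, but the documents give no SD, slope or correlation by arm, and the opposite ratio reverses the sign. The second is that the code contradicts the phrase *treatment-based*. It does not: SAP 12.1 itself explains that treatment is included as a variable, and neither document promises separate models by arm. The phrase is ambiguous.

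**Conclusion.** The structural point holds: SAP 12.1 imposes a common residual covariance and common baseline slopes on both arms, and the responder rule makes the imputed rates sensitive to spread. The direction of any bias cannot be told from the documents. Its size is about −0.6 to +0.4 point of a 25-point difference with 5% missing, and about −1.2 to +0.8 with 10%, for SD ratios of 0.5 to 2; it is zero when spreads and slopes are equal. These figures rest on normal changes, missingness unrelated to outcome and equal between arms, and the planned response rates. The trial's conclusion is very unlikely to change. This is a minor point, worth taking because the remedy is free and the wording needs settling anyway.

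**What to change.** Impute within randomized arm. Sort the input by `TRTPN`, add `BY TRTPN` to PROC MI, and take `TRTPN` out of the variable list, leaving `VAR VA40 VA40BL VA4 VA4BL`. Combine the two arms and sort by `_IMPUTATION_` before PROC LOGISTIC, so that each of the 25 completed data sets holds both arms. Do the same at the time points for H02 to H04. In SAP 12.1, state that *treatment-based* means imputation within randomized arm, and bring the sentence on imputation-model variables into line.

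The cost is a few lines of code and one or two SAP sentences, with no new data. The only statistical price is slightly wider imputation uncertainty, because each arm's covariance is estimated from its own subjects. With four variables and about 150 per arm this is negligible.
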